2.4. RANDOMIZATION

Subjects are randomly assigned in equal numbers (1:1) to one of two treatment arms:

- Perceval valve
- Standard sutured stented bioprosthetic aortic valve (control)

on the basis of a randomization list that has been performed before study start. Randomization list is stratified by 2 factors:

- country, and
- surgical approach (full sternotomy” or “mini-sternotomy”).

Only subjects who have undergone standard chest CT-scan to determine if the aortic stenosis can be replaced with an available Perceval valve, and is potentially suitable for mini-sternotomy, may be randomized. For each subject the randomization will be performed through eDC system after enrollment and before valve operation, specifically after CT scan and surgical approach (“full sternotomy” or “mini-sternotomy”) has been determined.

One patient will be considered adherent to the randomization if an attempt to implant of the allocated valve is performed. In case of, after an unsuccessful implant, a valve of the other arm is implanted the adherence to randomization allocation will be considered maintained.

3. DOCUMENT AND CHANGE HISTORY

3.1.CHANGES IN ANALYSIS COMPARED TO CLINICAL INVESTIGATIONAL PLAN

No changes in the analysis as described in the Clinical Investigational Plan.

3.2.SAP AMENDMENT RATIONALE AND CHANGE HISTORY

Table 2 : SAP Amendment description

Version	Date	Section(s)	Description of modifications
1.0	13MAR2017		Initial Release.
2.0	26JUL2017	7,9,10,10,13	Additional general details on how to represent values in the statistical analysis. Additional specifications have been added to analysis populations (including the definition of adherence to randomization allocation). Details on compliance calculation have been added. Additional derivation rules.
3.0	28JUN2018	10, 11, 12 Editorial changes impact all the document	SAP has been amended following the CIP amendment: 
 Adaptive design; Primary analysis; Sensitivity analysis. Details on primary analysis (Bayesian approach) have been added. Additional analysis for NYHA, echocardiographic data, EQ5D. Surgical times analysis has been modified from ANOVA to ANCOVA. Editorial changes (new template per internal SOP). List of TFLs have been removed (included in a different document).
4.0	16MAY2019	12.1.2, 12.2, 12.3, 13.4	Sensitivity analyses of Surgical times have been added; Additional details for checking the assumptions for ANCOVA; Additional details have been added for the calculation and testing of NCI and rNCI, including the management of missing data (if needed) and an analysis by country; Sensitivity analyses of EQ-5D-5L have been added (using France-based scoring system and with a Mann-Whitney test); The use of a discount rate for the QALY has been removed; Additional details on calculation of EQ-VAS have been added; Details on pacemaker evaluation through ECG Core Lab have been added.

5.0	01OCT2019	6.6, 8, 8.6, 11, 13.1.1, 13.1.2, 18.10, 18.12	
Usage of analysis populations have been updated.
 
Statistical tests and p-value have been added for comparison of baseline variables between treatment groups.
 
Site reported echocardiographic parameters have been updated.
 
Core-lab reported echocardiographic parameters have been updated.
 
In Cox regression model of MACCE, language has been modified to reflect that for the stratification factor of country, countries with less than 20 enrolled patients will be polled.
 
Summary of the number and percentage of subjects with AEs has been updated.
 
Summary of the number and percentage of TEAEs has been updated.
 
“Parivalvular leak” has been updated to be “central leak”.
 
Additional languages have been added for instructions on how to handle missing AE start date and stop date.
 
Data derivations have been updated.

-----	-----------	---	---

4. OVERVIEW OF PLANNED STATISTICAL ANALYSIS

The study plans for the different statistical analyses. The statistical analyses will be performed as detailed in this Statistical Analyses Plan (SAP). The SAP will be finalized prior to any interim analyses.

4.1. PRIMARY STATISTICAL ANALYSIS

The primary statistical analysis will be performed by Sponsor personnel once all the subjects complete their 12 month follow-up and the study database will be locked. This analysis will be focused on:

- primary endpoint
- mortality and morbidity rates up to 365 days
- other safety endpoints up to 12-months FU visit

The results of the primary statistical analysis will be the basis for a dedicated clinical study report.

4.2. INTERIM STATISTICAL ANALYSES

Interim analyses for accrual stopping will be conducted by an Independent Statistical Unit (ISU) composed by external statistical personnel not involved in the study conduct at the time when approximately 900 and 1050 patients are enrolled in the study. For details on the interim analysis please refer to Section 15.

4.3. OTHER STATISTICAL ANALYSIS

Safety monitoring analyses based on unclean data will be performed periodically with the involvement of Data Safety Monitoring Board (DSMB). The analysis will be descriptive in nature and no tests on the primary endpoint will be performed. Therefore no alpha adjustment for multiplicity is required.

The DSMB will be blinded to the actual treatment arms and will be responsible for monitoring the safety and well-being of the subjects participating in the trial, ensuring the scientific integrity of the trial, and recommending action items based on safety issues including trial termination as warranted. DSMB can be unblinded at any time during the study for safety reasons.

The first Safety monitoring analysis will be performed after first 200 subjects are enrolled. Subsequent analyses will be carried out approximately every 200 enrolled subjects.

4.4. FOLLOW-UP AND FINAL STATISTICAL ANALYSES

Follow-up statistical analyses will be performed by Sponsor personnel once per year once all the subjects complete their 2, 3, 4, and 5 years follow-up and the study database will be locked. The 5-year analysis will be considered as the final study analysis and will be the basis for the integrated clinical study report.

4.5. ADDITIONAL STATISTICAL ANALYSIS

Potential statistical analyses might be performed after Primary statistical analysis upon scientific purpose. Analyses will be detailed through an amendment to the SAP or a specific document.

Specific SAE listings that will contain all information in the SAE CRF needed to screen for CEC adjudicability will be created. These listings will be provided to the Safety Office and CPM upon requests and include:

- List of cases with CKMB/Troponin elevations as described in the adjudicability criteria
- List of EKG tracing results per visit
- List of mRS and NIHSS results for each patient per visit
- List of hemoglobin/hct; platelet count results; CRP results

5. ANALYSIS CONVENTION

5.1. GENERAL PRINCIPLES

The statistical analysis will be performed on the analysis study database with SAS version 9.4 or above (SAS Institute, Cary, N.C.), FACTS version 6.1 or above (Berry Consultants, Austin TX) or R version 3.3 or above.

All tabular and graphical presentations will be done by treatment group.

All the data collected and derived in the study will be presented in subject data listings.

5.2. DESCRIPTIVE STATISTICS

Descriptive statistics will be calculated using as reference the number of subjects in the relevant analysis population (any exception will be specified) according to the nature of the data as follows:

- Continuous variables: number of non-missing observations, arithmetic mean, standard deviation, minimum and maximum values, median and quartiles. If there are less than 5 observations, only the number of non-missing observations, arithmetic mean, median, minimum and maximum will be presented.
- Categorical variables: Number of missing and non-missing observations the relevant percentage on the analysis population. In case of subcategories, the relative frequencies will be calculated on the basis of the subjects in the subcategory, in this case a footnote will be added explaining the different denominators.
- Time-to-event variables: number of non-missing observations, minimum, first quartile, median including 95% confidence interval, third quartile, and maximum. For calculating the survival estimate CI bounds the log-log transformed estimate of CI bounds will be used. In addition, Kaplan-Meier estimates and plots will be provided with:
 - the 95% confidence interval bounds calculated per the method proposed by Greenwood⁸
 - the respective number of patients at risk and Kaplan-Meier estimates at different time points (at least every 5 months or more frequently)
 - the median and its 95% confidence interval.
 - the log-rank test p-value
 - the Hazard Ratio (HR), its 95% confidence interval and the relevant p-value.

Subjects ongoing and who are free from event at the analysis cut-off date will be censored at the analysis cut-off date. Subjects who have discontinued without an event will be censored at the date of discontinuation.

- For Bayesian analyses: posterior means, standard deviations, and 95% credible intervals will be reported.

5.3. SUBGROUPS DEFINITIONS

The following variables and levels will be considered for subgroup analyses:

- Gender (“Female” vs “Male”)
- Surgical approach (“Full sternotomy” vs “Mini-sternotomy”)
- Concomitant procedures (“Concomitant procedure” vs “Isolated procedure”)
- STS predicted risk of mortality (“Low risk [<4]” vs “Med/High risk [≥ 4]”)
- Regurgitation severity (“None/Trace” vs “Mild/Moderate/Severe”) at discharge
- Early (≤ 30 days) Post-implant permanent PaceMaker (“Yes” vs “No”)

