7.3. PROTOCOL DEVIATIONS

All protocol deviations (PDs) will be summarized overall (ENR) and by arm (ITT) by severity (minor and major) and grouped into different categories:

- Inclusion/Exclusion
- Informed Consent
- Procedure Performed by Unauthorized Physician
- Visit/Follow-up Not Done

- Visit/Follow-up Out of Window
- Assessment/Procedure Incomplete/Not Done
- Assessment/Procedure Out of Window
- Planned Surgical Approach Changed
- Randomization
- Study Device Not Used per IFU or per Protocol
- Serious Adverse Event Not Reported per Protocol
- Other

PDs will be reported as:

- total PDs on the total number of patients
- number of subjects with at least one PD on the total number of patients

Protocol deviations will be presented in a subject data listing.

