11. SECONDARY EFFICACY ANALYSES

The following secondary efficacy analyses will be performed:

- each component of the primary endpoint will be analyzed as binomial proportion (95% C.I.) of subjects event-free at one year (section 18.12);
- primary endpoint will be analyzed annually as binomial proportion (95% C.I.) of subjects event-free at 1, 2, 3, 4 and 5 years of follow-up (section 18.12);
- The time to the first MACCE will be analyzed using all data collected up to analysis cutoff date (patients may have more that 1-year follow-up):
 - by means of time-to-event methods (see section 5.2)
 - with a Cox regression model, using the stratification factors (country and surgical approach) and pre-operative variables (including demographic, medical history, and concomitant procedures) as covariates. Countries with less than 20 enrolled patients will be pooled. The assumptions of proportionality will also be investigated with a time-dependent exploratory variable, which is defined as $\text{treatment} * \{\log[\text{time to event}]\}$. If the p-value from the Wald Chi-squared statistic for this variable is less than 5% there is

evidence of a departure from the adjusted model assumptions. In case of non-proportional hazards, a Weibull model will be assumed as parametric form of the distribution of survival times. The treatment group will be included in the model as covariate.

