14. SUBGROUP ANALYSIS

The following analyses will be repeated for each subgroup (see section 5.3) using the same analysis population planned for each analysis:

- Subject disposition (section 0)

- Subject demographics (section 8.1), Implant characteristics (section 8.2), Valve characteristics (section 8.3), CT Scan (section 8.4), other baseline characteristics (section 8.6), and Healthcare Economics (section 8.8).
- Primary Endpoint (section 10).
- Forest plot showing the hazard ratio and 95% confidence intervals associated with variables considered in the multivariate analyses (treatment arm and all variables listed in section 5.3) with time to the primary endpoint (MACCE) as the dependent variable.
- Adverse Events (section 13.1)

TFLs will report per each subgroup level the overall and by treatment results. Analysis by subgroup will be performed if each subset has at least 15% of the allocated subjects.

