18.5. HANDLING OF MISSING VALUES

At each time point/visit, all subjects still in the study are reported. Missing values will be taken into account as missing in the analysis. The number of observed values and the number of missing values must sum up to the number of subjects in the study at the respective time point/visit.

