18.12. DATA DERIVATIONS

Table 8 : Data derivation rules

Derived variable	Derivation algorithm
Consented subject	Yes if filled date of consent No, otherwise.
Enrolled subject	Yes if filled date of consent AND patient is not a failure to implant (termination reason= FAILURE TO MEET RANDOMIZATION CRITERIA) No, otherwise.
ITT subject	Yes if Randomization date not empty No, otherwise.
mITT subject	Yes if ITT and the valve is a study valve (as listed in CRF). In case of "other" values, they have to be checked one by one with PM. No, otherwise.
Adherence to Randomization allocation	Yes if "Was the randomized valve implanted?" at first attempt=Yes No, otherwise.
SAF subject	Yes if Randomization and Implant dates not empty No, otherwise.
PP subject	Yes if 
 - Randomization and Implant dates not empty - Adherent to randomization - no major protocol violation (as reported in CRF field). No, otherwise.

Derived variable	Derivation algorithm
Operating room suite time (min)	Implant, Surgical time: Finish time – Start time
Skin-to-skin time (min)	Implant, Surgical time: Finish time – Start time
Extracorporeal circulation time (min)	Implant, Surgical time: Finish time – Start time
Cross clamp time (min)	Implant, Surgical time: Finish time – Start time
ICU stay (minutes)	Intensive Care Unit: [Date/Time of ICU Discharge] - [Date/Time of ICU Admission] If time of ICU discharge is missing it will be set at 23:59 If time of ICU Admission is missing it will be set at 00:00
ICU stay (days)	ICU stay (minutes) / 1440
Time to SAE	Serious Adverse Event (SAE): SAE start date – Surgery date +1
Early, Late SAE	EARLY if Time to SAE ≤ 30 days LATE if Time to SAE > 30 days

Derived variable	Derivation algorithm
Early safety (at 30 days)	
Serious Adverse Event (SAE):
 
YES if at least one (Time to SAE <=30 days) per CEC:
 
 - All-cause mortality - All stroke disabling and nondisabling - Life-threatening bleeding - Acute kidney injury—Stage 2 or 3 (including renal replacement therapy) - Coronary artery obstruction requiring intervention - Major vascular complication - Valve-related dysfunction requiring repeat procedure (BAV, TAVI, or SAVR): SVD and Aortic regurgitation requiring re-intervention 
NO, otherwise

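### Two of the six SAP subgroup variables (regurgitation at discharge, pacemaker within 30 days) arise after the valve is implanted, so the SAP 14 subgroup and forest-plot results for MACCE are not clean treatment comparisons

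*SAP*

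**What the plan says.** SAP 5.3 names six subgroup variables: gender, surgical approach, concomitant procedures, STS risk, "Regurgitation severity" at discharge (none/trace against mild or worse), and "Early (≤ 30 days) Post-implant permanent PaceMaker" (yes/no). CIP 8.5.7 places randomisation before the operation, so the last two are post-randomisation measurements.

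CIP 8.5.8 lists both as outcomes: pacemaker implantation is secondary endpoint 8, and aortic insufficiency and paravalvular leak, including at discharge, fall under endpoint 9. The pacemaker sub-study in CIP 8.5.9 records how each implant relates to the device.

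SAP 14 uses the 5.3 variables in two ways that matter here. It repeats the primary-endpoint analysis within each level, and it draws a forest plot from "multivariate analyses (treatment arm and all variables listed in section 5.3) with time to the primary endpoint (MACCE") as the outcome. Its only restriction is one of size: "Analysis by subgroup will be performed if each subset has at least 15% of the allocated subjects".

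The Cox model in SAP 11 is different. Besides treatment it uses the stratification factors and "pre-operative variables (including demographic, medical history, and concomitant procedures) as covariates". On timing, SAP 18.12 counts events from the operation ("SAE start date – Surgery date +1"), and SAP 18.5 says "Missing values will be taken into account as missing in the analysis".

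**The concern.** A subgroup variable keeps the randomised comparison intact only if the treatment cannot have affected it. Leak at discharge and early pacing may well depend on which valve was implanted. That creates three problems.

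- **Non-randomised groups.** Perceval and control patients who share a leak or pacemaker level need not be alike in other respects. Conditioning on that level brings in differences through shared causes such as frailty.
- **Masking.** If the valve raised MACCE through pacing or leak, adjusting for these variables would remove that part of the effect from the treatment row.
- **Timing.** MACCE counts from surgery, but pacemaker status can be fixed as late as day 30. Patients who die before pacing fall into the unpaced group (immortal time). Patients who die before discharge have no discharge echo and may drop out of the model (selection).

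The bias requires that the valve changes these variables and that they cause MACCE or share causes with it. What is at stake is the reading of the by-leak and by-pacemaker MACCE results and of the forest plot's treatment hazard ratio.

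**Working it through.** **The plan's size rule.** 15% of 900, 1050 and 1234 is 135, 157.5 and 185.1, so each subset needs at least 135, 158 or 186 patients. The documents give no expected pacemaker rate. Pooled rates of 7.5% or 10% would give about 93 or 123 of 1234, and the pacemaker split would be cancelled. A pooled 20% with mild or worse regurgitation gives about 247, and that split would go ahead.

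**Assumptions for the bias figures (not in the documents).** No true valve effect; 30% frail patients with 18% MACCE and 70% others with 5%. Each arm then has 0.3 × 0.18 + 0.7 × 0.05 = 8.9%. Frail patients are k times as likely to be paced or to leak. The Perceval excess is spread as an equal absolute amount, as an equal relative amount, or only among the frail.

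**1. Adjusting for pacemaker.** Worked case: 5% vs 10% paced, k = 3, equal relative excess. Frail/other pacing is 9.375%/3.125% in control and 18.75%/6.25% in Perceval.

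| Stratum | Control: share, MACCE | Perceval: share, MACCE |
|---|---|---|
| Paced | 0.05, 0.006156 | 0.10, 0.012313 |
| Unpaced | 0.95, 0.082844 | 0.90, 0.076688 |

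Mantel-Haenszel ratio = (0.012313 × 0.05/0.15 + 0.076688 × 0.95/1.85) ÷ (0.006156 × 0.10/0.15 + 0.082844 × 0.90/1.85) = 0.04348/0.04441 = 0.979. The true ratio is 1.00.

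Over k = 2, 3, 4 and the three ways of spreading the excess:

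| Paced, control vs Perceval | Adjusted ratio |
|---|---|
| 5% vs 5% | 1.00 |
| 5% vs 10% | 0.964–0.991 |
| 5% vs 15% | 0.915–0.987 |

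**2. Masking.** With 8.5% MACCE if unpaced and double that if paced, the true ratio at 5% vs 10% is (0.085 × 1.10)/(0.085 × 1.05) = 1.048. Within pacemaker strata it is 1.00.

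**3. Splitting on regurgitation.** Mild or worse in 15% vs 25%, k = 2. Control risks are 11.0% (mild or worse) and 8.53% (none/trace).

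| Spread of excess | Mild or worse: Perceval risk, ratio | None/trace: Perceval risk, ratio |
|---|---|---|
| Equal absolute | 10.16%, 0.92 | 8.48%, 0.99 |
| Equal relative | 11.0%, 1.00 | 8.20%, 0.96 |
| Frail only | 13.8%, 1.255 | 7.27%, 0.85 |

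**4. Proportional-hazards check with both variables in the model.** Assumed: pacing 4% vs 10%, regurgitation 10% vs 20%, frailty in 30%, control MACCE 9%. With frailty odds ratios and hazard ratios of 2 to 5 and no true valve effect, the adjusted hazard ratio is 0.98 down to 0.90. With no frailty and each variable raising the hazard 1.5- to 3-fold, a total hazard ratio of 1.08 to 1.27 appears as 1.00. If the valve affects neither variable, there is no bias.

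**5. Early deaths.** CIP 6.2 cites early or 30-day mortality of 1.8% to 3.4%. At 9% MACCE and N = 1234 that is 22 to 42 of about 111 events (20–38%). Let e be the proportion who die before they could be paced, with 7.5% paced and later MACCE unrelated to pacing. Paced risk is q = (0.09 − e)/(1 − e); unpaced risk is (0.09 − 0.075q)/0.925.

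- e = 0.009 (half of 1.8%): q = 0.0817, unpaced 0.0907, ratio 0.90.
- e = 0.034 (all of 3.4%): q = 0.0580, unpaced 0.0926, ratio 0.63.

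This distorts the pacemaker row, not the treatment row.

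**6. Dropping patients without a discharge echo.** With assumed in-hospital mortality of 2% vs 4% and 7% later MACCE, the true difference in event-free rate is 0.98 × 0.93 − 0.96 × 0.93 = 0.0186. Among patients with an echo it is zero.

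**The case against.** The strongest reply is that little depends on SAP 14. No alpha, claim or stopping rule is attached to it. SAP 11 already supplies a hazard ratio adjusted only for stratification factors and pre-operative variables, and the forest plot can be read as a prognostic display. That is right about reach. However, SAP 14 does not call these outputs exploratory or warn the reader that the treatment row has a different meaning there.

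The 15% rule would probably cancel the pacemaker split. It does not clearly govern the multivariable model: the forest plot is one item under the repeated subgroup analyses, the rule closes the section, and the model text still calls for every 5.3 variable. The rule may also let the regurgitation split through.

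On missing echoes, SAP 11.2.2 plans multiple imputation of leak severity, so patients need not be lost. Nothing links those imputed data to SAP 14, so it remains open whether they would be. A literal reading of the per-protocol definition in SAP 6.5 could exclude early deaths through its visit-attendance condition. The SAP 18.12 derivation omits that condition, and SAP 6.6 also plans the primary endpoint in the mITT population.

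The numbers deserve caution. With about 111 events the standard error of a log hazard ratio is near 2/√111 = 0.19, a 95% factor of about 1.45 each way, so a shift to 0.96–0.99 is small against noise. The 0.915 extreme needs about 44% of frail Perceval patients paced against 2.6% of the others, which is not realistic. The early-death bound sets mortality from earlier Perceval trials against this trial's 9% MACCE rate. With the 12% implied by the 88% from CAVALIER, the 0.63 becomes (0.086/0.966)/0.1225 = 0.73. These points limit the size and leave the structural fault standing.

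**Conclusion.** The concern holds. Two of the six subgroup variables are post-randomisation outcomes, and SAP 14 stratifies and adjusts the MACCE comparison on them without a landmark or caveat, although SAP 11 keeps to pre-operative variables.

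Under the stated assumptions the distortion of the treatment row is small to moderate, and it is zero if the valve affects neither variable. The regurgitation split can be off by more, in either direction. Masking matters most in a trial that tests safety as well as efficacy: harm acting through pacing or leak would disappear from the adjusted treatment row. Every pacing, leak and frailty rate is assumed, and only the early mortality figures come from the CIP.

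The confirmatory Bayesian test (SAP 10.3), its type I error and power, and the SAP 10.4 sensitivity analyses do not use these variables. The change should be made, but the primary conclusion does not depend on it.

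**What to change.** Remove discharge regurgitation and early pacemaker from the primary-endpoint subgroups and from the SAP 14 multivariable MACCE model. Keep gender and STS risk. Keep surgical approach and concomitant procedures as planned before randomisation: SAP 7.3 has a deviation category "Planned Surgical Approach Changed", so the planned and actual approach can differ.

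Report leak and pacemaker as outcomes by arm. If their association with later MACCE is of interest, use a day-30 landmark or a time-dependent covariate and label the result as non-randomised. Any adverse-event tables kept by these two variables should carry the same label.

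The cost is SAP wording, with two exploratory displays lost or relabelled. Data collection, sample size, type I error and power do not change.
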